7.2. Screening and Critical Baseline Assessments

Cardiovascular medical history/risk factors (as detailed in the eCRF) will be assessed at screening.

The following demographic parameters will be captured: year of birth, sex, race, and ethnicity.

Medical/medication/family history will be assessed as related to the inclusion/exclusion criteria listed in Section 5.

7.3. Safety

Planned time points for all safety assessments are listed in the Time and Events Table (Table 9). Additional time points for safety tests such as vital signs, physical exams, and laboratory safety tests may be added during the course of the study based on newly available data to ensure appropriate safety monitoring.

7.3.1. Adverse Events and Serious Adverse Events

The definitions of an AE or SAE can be found in [Appendix 5](#).

The investigator and their designees are responsible for detecting, documenting, and reporting events that meet the definition of an AE or SAE.

7.3.1.1. Time Period and Frequency for Collecting Adverse Event and Serious Adverse Event information

- Any SAEs assessed as related to study participation (e.g., protocol-mandated procedures, invasive tests, or change in existing therapy) or related to a GSK product will be recorded from the time a subject consents to participate in the study up to and including any follow-up contact.
- AEs will be collected from the time informed consent is obtained until the follow-up contact (see Section 7.3.1.3), at the time points specified in the Time and Events Table (Table 9).
- Medical occurrences that begin prior to the start of study treatment but after obtaining informed consent may be recorded on the Medical History/Current Medical Conditions section of the eCRF.
- All SAEs will be recorded and reported to GSK within 24 hours, as indicated in [Appendix 5](#).
- Investigators are not obligated to actively seek AEs or SAEs in former study subjects. However, if the investigator learns of any SAE, including a death, at any time after a subject has been discharged from the study, and he/she considers the event reasonably related to the study treatment or study participation, the investigator must promptly notify GSK.

NOTE: The method of recording, evaluating and assessing causality of AEs and SAEs plus procedures for completing and transmitting SAE reports to GSK are provided in [Appendix 5](#).

7.3.1.2. Method of Detecting Adverse Events and Serious Adverse Events

Care will be taken not to introduce bias when detecting AEs and/or SAEs. Open-ended and nonleading verbal questioning of the subject is the preferred method to inquire about AE occurrence. Appropriate questions include:

- “How are you feeling?”
- “Have you had any (other) medical problems since your last visit/contact?”
- “Have you taken any new medicines, other than those provided in this study, since your last visit/contact?”

7.3.1.3. Follow-Up of Adverse Events and Serious Adverse Events

After the initial AE/SAE report, the investigator is required to proactively follow each subject at subsequent visits/contacts. All SAEs, and non-serious AEs of special interest (as defined in Section [4.6.1](#)) will be followed until resolution, until the condition stabilizes, until the event is otherwise explained, or until the subject is lost to follow-up (as defined in Section [5.4](#)). Further information on follow-up procedures is given in [Appendix 5](#).

7.3.1.4. Regulatory Reporting Requirements for Serious Adverse Events

Prompt notification by the investigator to GSK of SAEs related to study treatment (even for noninterventional post marketing studies) is essential so that legal obligations and ethical responsibilities towards the safety of subjects and the safety of a product under clinical investigation are met.

GlaxoSmithKline has a legal responsibility to notify both the local regulatory authority and other regulatory agencies about the safety of a product under clinical investigation. GlaxoSmithKline will comply with country specific regulatory requirements relating to safety reporting to the regulatory authority, IRB/IEC, and investigators.

Investigator safety reports are prepared for suspected unexpected serious adverse reactions according to local regulatory requirements and GSK policy and are forwarded to investigators as necessary.

An investigator who receives an investigator safety report describing a SAE(s) or other specific safety information (e.g., summary or listing of SAEs) from GSK will file it with the IB and will notify the IRB/IEC, if appropriate according to local requirements.

7.3.2. Pregnancy

Details of all pregnancies in female subjects and, if indicated, female partners of male subjects will be collected after the start of dosing and until the Follow-up visit.

If a pregnancy is reported then the investigator should inform GSK within 2 weeks of learning of the pregnancy and should follow the procedures outlined in [Appendix 7](#).

7.3.3. Physical Exams

A complete physical examination will include, at a minimum, assessment of the cardiovascular, respiratory, GI, and neurological systems. Height and weight will also be measured and recorded.

A brief physical examination will include, at a minimum, assessments of the skin, lungs, cardiovascular system, and abdomen (liver and spleen).

Investigators should pay special attention to clinical signs related to previous serious illnesses.

7.3.4. Vital Signs

Vital signs will be measured in semi-supine position after 5 minutes rest and will include systolic and diastolic blood pressure, and heart rate. Body temperature and respiratory rate will be collected at Screening only.

7.3.5. Electrocardiogram

TriPLICATE 12-lead ECGs will be measured in semi-supine position after 5 minutes rest and obtained at least 5 minutes apart on Day -1. Single 12-lead ECGs will be measured in semi-supine position after 5 minutes rest at all other time points during the study using an ECG machine that automatically calculates the heart rate and measures PR, QRS, QT, and QTc intervals. Refer to Section [5.4.2](#) for QTc stopping criteria and additional QTc readings that may be necessary.

7.3.6. Clinical Safety Laboratory Assessments

All protocol-required laboratory assessments, as defined in [Table 10](#), must be conducted in accordance with the Laboratory Manual, and Protocol Time and Events Table ([Table 9](#)). Laboratory requisition forms must be completed and samples must be clearly labelled with the subject number, protocol number, site/center number, and visit date. Details for the preparation and shipment of samples will be provided by the laboratory and are detailed in the SRM. Reference ranges for all safety parameters will be provided to the site by the laboratory responsible for the assessments.

If additional non-protocol specified laboratory assessments are performed at the institution's local laboratory and result in a change in subject management or are considered clinically significant by the investigator (e.g., SAE or AE or dose modification) the results must be recorded in the eCRF.

Refer to the SRM for appropriate processing and handling of samples to avoid duplicate and/or additional blood draws.

Hematology, clinical chemistry, urinalysis and additional parameters to be tested are listed in [Table 10](#).

Table 10 Protocol-Required Safety Laboratory Assessments

Hematology			
Platelet count	RBC indices:	WBC count with differential:	
RBC count	MCV	Neutrophils	
Hemoglobin	MCH	Lymphocytes	
Hematocrit	MCHC	Monocytes	
		Eosinophils	
		Basophils	
Serum Chemistry^a			
Blood urea nitrogen	Potassium	Aspartate aminotransferase	Total and direct bilirubin
Creatinine	Sodium	Alanine aminotransferase	Total protein
Glucose	Calcium	Alkaline phosphatase	Albumin
Creatine kinase	Bicarbonate	Chloride	
Routine Urinalysis			
Specific gravity			
pH, glucose, protein, blood, and ketones by dipstick			
Microscopic examination (if blood or protein is abnormal)			
Other Screening Tests			
Hepatitis B surface antigen, hepatitis C antibody, and human immunodeficiency virus			
Follicle-stimulating hormone and estradiol (as needed in women of nonchildbearing potential only)			
Serum test for human chorionic gonadotropin (as needed in women of childbearing potential)			
Alcohol (via urine, blood alcohol, or breathalyzer test), cotinine, and drug screen (via serum, urine, or saliva) to include, at a minimum: amphetamines, barbiturates, cocaine, opiates, cannabinoids, and benzodiazepines).			
Fecal occult blood test and stool cultures as appropriate for gastrointestinal adverse events (Appendix 8)			

MCH = mean corpuscular hemoglobin; MCHC = mean corpuscular hemoglobin concentration; MCV = mean corpuscular volume; RBC = red blood cell; WBC = white blood cell.

^a Details of liver chemistry stopping criteria and required actions and follow-up assessments after liver stopping or monitoring event are given in Section [5.4.1](#) and [Appendix 3](#).

All laboratory tests with values that are considered clinically significantly abnormal during participation should be repeated until the values return to normal or baseline. If such values do not return to normal within a period judged reasonable by the investigator, the etiology should be identified and the sponsor notified.

7.4. Pharmacokinetics

7.4.1. Blood Sample Collection

Blood samples for PK analysis of gepotidacin will be collected at the time points indicated in the Time and Events Table ([Table 9](#)). The actual date and time of each blood sample collection will be recorded. The timing of PK samples may be altered and/or PK samples may be obtained at additional time points to ensure thorough PK monitoring.

For each sample, 3 mL of blood will be drawn via an indwelling catheter and/or direct venipuncture into tubes containing ethylenediaminetetraacetate anticoagulant. Details of PK blood sample processing, storage, and shipping procedures are provided in the SRM.

7.4.2. Urine Sample Collection

Pharmacokinetic urine samples for the analysis of gepotidacin (Parts 1a, 2, and 3 only) will be collected at the time points listed in the Time and Events Table ([Table 9](#)). The actual date and time of each urine sample collection will be recorded. The timing of PK samples may be altered and/or PK samples may be obtained at additional time points to ensure thorough PK monitoring.

Details of PK urine sample processing, storage, and shipping procedures are provided in the SRM.

7.4.3. Sample Analysis

Plasma and urine analysis will be performed under the control of PTS-DMPK/Scinovo, GSK, the details of which will be included in the SRM. Concentrations of gepotidacin will be determined in plasma and urine samples using the currently approved bioanalytical methodology. Raw data will be archived at the bioanalytical site (detailed in the SRM).

Since plasma protein binding of gepotidacin is low (33%), only total drug concentrations will be reported for the PK analysis.

Once the plasma and urine samples have been analyzed for gepotidacin, any remaining plasma and urine samples may be analyzed for other compound-related metabolites and the results reported under a separate PTS-DMPK/Scinovo, GSK protocol.

7.5. Genetics

Depending on the clinical study results, exploratory pharmacogenomics analyses may be performed to examine the potential relationship between genetic variants and clinical endpoints.

The pharmacogenomics samples will be collected according to the Time and Events Table ([Table 9](#)). Information regarding genetic research is included in [Appendix 4](#).

8. DATA MANAGEMENT

- For this study, subject data will be entered via an eCRF into Oracle Clinical Remote Data Capture System. Subject data will be available for viewing through access to the Oracle Clinical Remote Data Capture System. Data provided from other sources will be received, reconciled, combined, and transferred to GSK at predetermined time points.
- Management of clinical data will be performed in accordance with applicable PPD standards and data cleaning procedures to ensure the integrity and quality of the data (e.g., removing errors and inconsistencies in the data). Adverse events and concomitant medications terms will be coded using Medical Dictionary for Regulatory Activities (MedDRA) and a validated medication dictionary, GSKDrug.

- The eCRFs (including queries and audit trails) will be sent at the end of the study in electronic format to GSK to be retained. Each investigator will receive a copy of their site specific data in the same format to maintain as the investigator copy. In all cases, subject initials will not be collected or transmitted.

9. STATISTICAL CONSIDERATIONS AND DATA ANALYSES

All statistical analyses will be performed by PPD using SAS (SAS Institute Inc., Cary, North Carolina, USA), version 9.2 or higher. Pharmacokinetic parameters will be calculated using Phoenix WinNonlin (Certara USA Inc., Princeton, New Jersey, USA), version 6.2.1 or higher.

Before database lock, a reporting and analysis plan (RAP) will be issued as a separate document, providing detailed methods for the analyses outlined below.

Any deviations from the planned analyses will be described in a RAP addendum and justified in the final integrated clinical study report.

9.1. Hypotheses

A formal hypothesis will not be tested; however, an estimation approach will be taken to characterize the relative bioavailability of the gepotidacin RC and HSWG tablet formulations relative to the reference gepotidacin capsule formulation in healthy subjects (Part 1a), estimate the effect of food on the tablet formulation selected from Part 1a (Part 1b), and to evaluate the pharmacokinetics of the tablet formulation selected from Part 1a in Japanese subjects (Parts 2 and 3).

9.2. Sample Size Considerations

9.2.1. Sample Size Assumptions

Sample size is largely based on feasibility; however, some justification is provided below.

Part 1a – Relative Bioavailability:

The sample size of 24 PK parameter population subjects will be used based on feasibility to address the objectives of Part 1a of the study.

There are no estimates for the coefficient of variation (CV) of HSWG for any PK parameters. An assumed CV of 27.5% for a PK parameter implies that the sample size of 24 PK parameter evaluable subjects will provide at least 80% power to demonstrate equivalence of the PK parameter. Equivalence is demonstrated when 90% confidence interval (CI) for the ratio of Test:Reference of the PK parameter will be within 0.8 to 1.25 following log transformation.

Two different test formulations are being used in this study. No adjustment for pre-planned multiple comparisons are made.

The total sample size of 27 subjects (9 subjects in 3 sequences) will be randomized to ensure 24 PK parameter evaluable subjects with PK parameter estimates from the reference and at least one test formulation.

Part 1b – Food Effect:

A sample size of 16 subjects will be randomized (8 per sequence) based on feasibility to address the objectives of Part 1b of the study.

This sample size will ensure equivalence (as specified in sample size assumption in Part 1a) with 80% power with an assumed CV of 22%.

Part 2 – Pharmacokinetics:

A sample size of approximately 10 subjects will be used in Part 2 based on feasibility to address the objectives of Part 2 of the study.

Part 3 – Pharmacokinetics - Fed State:

A sample size of 12 subjects (ideally 6 male, 6 female) will be randomized (10 active: 2 placebo) based on feasibility to address the objectives of Part 3 of the study.

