9.3.2. Interim Analysis

No formal interim analyses are planned for this study. However, all preliminary safety, tolerability, and available PK data will be reviewed by the study team after completing Part 1a of the study to select the formulation for Part 1b, Part 2, and Part 3, and also to

determine if the effect of food on the selected formulation needs to be studied (Part 1b). At the time of finalization of Protocol Amendment 1, Part 1b is no longer needed based on data from Part 1a. The team will review unblinded data from Part 1a of this open-label study to select the appropriate formulation.

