The log-transformed AUC(0-∞), AUC(0-t), and Cmax values for gepotidacin will be analyzed separately using a mixed effects model as appropriate to the study design, fitting fixed-effect terms for sequence, period, and regimen, and treating subject within sequence as a random effect. Point estimates and 90% CIs for the differences of interest (RC tablets and HSWG tablets versus capsules) will be constructed using the residual variance. Point and interval estimates will then be exponentially back-transformed to construct point and 90% CI estimates for the ratios of interest (RC tablets and HSWG tablets versus capsules).

Estimates of within-subject variability for AUC(0-∞), AUC(0-t), and Cmax of gepotidacin will be provided, where:

$$CVw (\%) = \text{sqrt}(\exp[MSE] - 1) \times 100$$

and MSE is the residual mean squared error from the model. CVw(%) represents a pooled measure of within-subject variability across regimens.

Distributional assumptions will be assessed by residual plots. Homogeneity of variance will be assessed by plotting the residuals against the predicted values from the model, whilst normality will be examined by normal probability plots. If assumptions are grossly violated, alternative analyses will be considered.

For the bioavailability assessment, Tmax will be analyzed nonparametrically using the Wilcoxon signed-rank test to compute the point estimate and 90% CI for the median difference for each comparison of interest.

For Parts 2 and 3, dose proportionality of AUC(0-∞) and Cmax will be explored separately and/or pooled together as a single model based on dose normalized parameters (log transformed parameters) using reference dose. The lower dose group (1500 mg) would be chosen as the reference dose.

The dose proportionality of AUC(0-∞) and Cmax will be summarized by descriptive statistics (including 90% confidence interval).

Detailed descriptions of the analyses in this study will be presented in the RAP.

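### Protocol Section 9.2.1 claims 80% power that its own inputs do not give: 24 evaluable at CV 27.5% yields about 76%, and 16 subjects at CV 22% about 73%

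*Protocol*

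**What the plan says.** Protocol Section 9.2.1 describes the sample sizes as largely a matter of feasibility and then offers power as supporting justification. Equivalence means that the 90% confidence interval for Test:Reference, after log transformation, lies within 0.8 to 1.25.

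- **Part 1a.** The input is "An assumed CV of 27.5% for a PK parameter", from which the section concludes that "the sample size of 24 PK parameter evaluable subjects will provide at least 80% power to demonstrate equivalence". On recruitment it plans 27 subjects, 9 in each of 3 sequences, and gives the purpose of that number as "to ensure 24 PK parameter evaluable subjects with PK parameter estimates from the reference and at least one test formulation".
- **Part 1b.** For 16 subjects, 8 per sequence: "This sample size will ensure equivalence (as specified in sample size assumption in Part 1a) with 80% power with an assumed CV of 22" per cent.

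The section does not give the assumed true ratio, the power method, or whether the CV is within- or between-subject. Section 9.4.1 builds the intervals from the residual variance and reports a CVw that "represents a pooled measure of within-subject variability across regimens". SAP Appendix 9 (Section 10.9.1) specifies Kenward-Roger degrees of freedom, so the planned intervals are t-based.

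**The concern.** The rule, sample sizes, CVs and designs are all given, so the power can be checked. A 90% interval built on residual variance in a crossover needs a within-subject CV as its input. On that reading both statements look too high even when the products are assumed identical. The Part 1a sentence claims a minimum, so any shortfall makes it wrong as written.

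Two features add to this. A true ratio other than 1.00 lowers the power further. Also, the 24 subjects need the reference and only one of the two test formulations, so a single tablet-versus-capsule contrast may rest on fewer than 24.

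What is at stake is how the Part 1a intervals are read. Someone told that the study had at least 80% power will take an interval that crosses 0.80 or 1.25 as stronger evidence of a formulation difference than the design supports.

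**Working it through.** **Inputs**

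| Input | Part 1a | Part 1b | Source |
|---|---|---|---|
| Subjects | 24 evaluable (27 randomised) | 16 | Protocol 9.2.1 |
| CV | 27.5% | 22% | Protocol 9.2.1 |
| Limits | ln 0.8 and ln 1.25 = ±0.2231 | same | Protocol 9.2.1 |
| Error rate | 90% CI = two one-sided tests at 0.05 | same | Protocol 9.2.1 |
| Design | 3-period, 3-sequence crossover | 2-period, 2-sequence crossover | Protocol 4.1 |
| Error term | residual variance, t-based | same | Protocol 9.4.1; SAP 10.9.1 |
| True ratio | not stated; 1.00 assumed, 0.95 and 1.05 also run | same | assumption |
| CV type | not stated; within-subject assumed | same | assumption, consistent with 9.4.1 |

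**Formulas**

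- Log-scale SD: σ = √ln(1 + CV²).
- Standard error of a treatment difference: SE = σ√(2/n).
- Residual df: Part 1a, 3n − n − 2 − 2 = 2n − 4. Part 1b, 2n − n − 1 − 1 = n − 2.
- Power: the probability that both confidence limits fall inside ±0.2231, integrated over the chi-square distribution of the estimated residual variance.

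**Part 1a**

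σ = √ln(1 + 0.275²) = 0.2700. At n = 24, SE = 0.2700 × √(2/24) = 0.0779 on 44 df.

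| Evaluable n | df | Power at 1.00 | Power at 0.95 |
|---|---|---|---|
| 24 | 44 | 75.9% | 66.6% |
| 25 | 46 | 78.3% | 68.7% |
| 26 | 48 | 80.4% | 70.7% |
| 27 | 50 | 82.3% | 72.5% |

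At a ratio of 1.05, n = 24 gives 67.5%. With pairwise df of n − 2, n = 24 gives 74.1%, n = 26 gives 78.8% and n = 27 gives 80.9%. The largest CV that gives 80% at a ratio of 1.00 is 26.4% with n = 24 and 28.2% with n = 27 (both on 2n − 4 df).

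**Part 1b**

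σ = √ln(1 + 0.22²) = 0.2174. At n = 16, SE = 0.2174 × √(2/16) = 0.0769 on 14 df. Power is 73.5% at 1.00, 64.4% at 0.95 and 65.3% at 1.05. At 1.00, n = 17 gives 77.3% and n = 18 gives 80.7%. The largest CV that gives 80% with n = 16 is 20.7%.

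**Attempts to recover the stated 80%**

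- *Large-sample normal formula*, 2Φ(0.2231/SE − 1.645) − 1. Part 1a: 0.2231/0.0779 = 2.86, giving 77.7%. Part 1b: 0.2231/0.0769 = 2.90, giving 79.2%.
- *One one-sided test only, or an 80% interval.* Each gives about 87% in both parts, but neither is the stated rule.
- *CV read as total CV.* An intrasubject correlation of about 0.1 gives 81.5% (Part 1a) and 79.3% (Part 1b). The documents state no correlation.

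Simulation agrees with the integration: 75.6% for the 3×3 model at n = 24 and 73.4% for the 2×2 at n = 16.

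**Fewer than 24 on one contrast**

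Suppose, for illustration, that 24 subjects all have the reference but two of them, in different sequences, lack one tablet. Keeping those two in the planned model leaves 42 residual df. Power is about 72% for the affected contrast and still about 76% for the other.

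**The case against.** The strongest reply has four parts.

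1. **Part 1b may be a large-sample figure.** The normal formula gives 79.2%, which rounds to what is stated, and the Part 1b sentence does not claim a minimum. That is a plausible origin. But the planned analysis is t-based on 14 residual df, where the figure is 73.5%, and the same formula still leaves Part 1a at 77.7%.
2. **The CV type is not stated.** Section 9.4.1 defines CVw for reporting and does not say that the 27.5% is that quantity. This stands as a caveat: the shortfall depends on the within-subject reading. The alternative needs a correlation that appears nowhere in the documents, and it does not suit intervals built on residual variance.
3. **27 are randomised.** With none lost, power at a ratio of 1.00 is 82.3%. That is correct, but the protocol uses the 27 only as an allowance to secure 24 and attaches its 80% to the 24.
4. **Little follows from it.** Sizing is largely by feasibility; "A formal hypothesis will not be tested; however, an estimation approach will be taken"; the formulation is chosen on PK, safety and tolerability together; and Section 9.3.2 records that "Part 1b is no longer needed based on data from Part 1a". Part 1a data were therefore in hand by Amendment 1. All of this stands and limits the weight of the point, but it does not make the stated power right.

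**Conclusion.** The concern holds, as a minor point. Against the stated 80%, Part 1a falls short by 80 − 75.9 = 4.1 points and Part 1b by 80 − 73.5 = 6.5 points, for one parameter and one contrast. At a true ratio of 0.95 the gaps are 13.4 and 15.6 points. The result assumes a within-subject CV and the t-based analysis in the SAP. The choice of true ratio cannot rescue the statements, because 1.00 is the best case. The Part 1a conclusion is the firmer of the two, since it survives the normal approximation; the Part 1b gap nearly closes under it. The number randomised to Part 1a is adequate for 80% at a ratio of 1.00 if at least 26 are evaluable (27 on n − 2 df).

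**What to change.** Keep the sample sizes and correct Section 9.2.1. Suggested text:

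- **Part 1a.** *With 24 subjects evaluable for a given Test-Reference contrast, a within-subject CV of 27.5% and a true ratio of 1.00, power is about 76% (about 67% at a true ratio of 0.95). If all 27 randomised subjects are evaluable, it is about 82% at a true ratio of 1.00. With 24 evaluable, 80% power holds for a within-subject CV up to 26.4%.*
- **Part 1b**, if its text is kept. *With 16 subjects, a within-subject CV of 22% and a true ratio of 1.00, power is about 73%; 80% holds for a CV up to 20.7%.*

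In both, state the true ratio, the CV type and that the calculation is t-based. Counting the 24 separately for each contrast is a useful clarification but is not essential to the correction.

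The cost is wording in one section. Subjects, analyses and decisions do not change; the stated power becomes slightly less favourable.

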Part 1b is a 2-period, cross-over study and will evaluate the effect of food on the safety, tolerability, and pharmacokinetics of a single dose of 1500 mg gepotidacacin tablet formulation selected from Part 1a. If both formulations of the free base tablet exhibit similar bioavailability to the capsule formulation, then the results of the moderate fat meal evaluated in the RC mesylate tablet formulation from Study BTZ117349 (GlaxoSmithKline Document Number [2013N176846_01](#) Study ID BTZ117349) will be used to guide dosing recommendations with food. See the study schematic in [Table 2](#) for more details.

Subjects will participate in 2 treatment periods and blood samples will be collected for PK analysis of gepotidacacin concentrations according to the Time and Events Table ([Table 9](#)). Blood samples will be collected up to approximately 48 hours after dosing.

Table 2 Part 1b Food Effect Study Design Schematic

Treatment	Cross-over			Follow-up
	Period 1	Wash-out At least 3 days	Period 2	
RC or HSWG tablet fasted ^a				5 to 7 days after final dose
RC or HSWG tablet fed ^a				
Sequence 4	D		E	
Sequence 5	E		D	

HSWG = high shear wet granulation; RC = related compound.

^a 1500 mg single dose given as 2 × 750 mg tablets fasted (Treatment D) and fed (Treatment E)

Part 2: Pharmacokinetics in Japanese Subjects

Part 2 is a 2-period, fixed-sequence study and will evaluate the pharmacokinetics of a single dose of 1500 mg followed by a single dose of 3000 mg gepotidacacin tablet formulation selected from Part 1a in a cohort of Japanese subjects under fasted conditions. See the study schematic in [Table 3](#) for more details.

Subjects will participate in 2 treatment periods and blood and urine samples will be collected for PK analysis of gepotidacin concentrations according to the Time and Events Table ([Table 9](#)). Blood and urine samples will be collected up to approximately 48 hours after dosing.

Table 3 Part 2 Pharmacokinetic Study Design Schematic

Treatment	Fixed-sequence				Follow-up
RC or HSWG tablet ^a	Period 1	Wash-out At least 3 days	Period 2	Wash-out At least 3 days	5 to 7 days after final dose
Sequence 6	B or C		F		

HSWG = high shear wet granulation; RC = related compound.

^a 1500 mg single dose given as 2 × 750-mg RC (Treatment B) or HSWG (Treatment C) tablets; 3000 mg single dose given as 4 × 750-mg RC or HSWG tablets (Treatment F)

Part 3: Pharmacokinetics in Japanese Subjects - Fed State

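### Section 9.2.1 claims 80% power for Part 1a without naming a true tablet:capsule ratio; at the stated CV and 24 subjects, power is about 74–76% even if exposure is identical, and lower at any other ratio

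*Protocol*

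**What the plan says.** Protocol Section 9.2.1 (Amendment 2) first says that the sample sizes rest mainly on feasibility, then offers a justification. For Part 1a it notes that "There are no estimates for the coefficient of variation (CV) of HSWG for any PK parameters". Taking the CV to be 27.5%, it concludes: "the sample size of 24 PK parameter evaluable subjects will provide at least 80% power to demonstrate equivalence of the PK parameter". The success rule is explicit: "Equivalence is demonstrated when 90% confidence interval (CI) for the ratio of Test:Reference of the PK parameter will be within 0.8 to 1.25", after log transformation. On numbers, "The total sample size of 27 subjects (9 subjects in 3 sequences) will be randomized to ensure 24 PK parameter evaluable subjects". Evaluable here means having PK parameters for the capsule and for at least one of the two tablets. On the two tablet comparisons, "No adjustment for pre-planned multiple comparisons are made".

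Neither this section nor any other part of the protocol states the true Test:Reference ratio assumed for the calculation. The SAP has no sample-size section and supplies none.

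Three other places set the context. Section 9.1 declares an estimation approach with no formal hypothesis. Section 4.1 makes the optional food-effect part (Part 1b) depend on the condition "If both formulations of the free base tablet exhibit similar bioavailability to the capsule formulation". Section 4.5, Table 6, gives geometric means for a 1500-mg capsule and a 1500-mg RC tablet, both fasted, from Study BTZ117349.

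**The concern.** Power to show equivalence depends on three inputs: variability, sample size and the true ratio. Section 9.2.1 supplies two and presents the power as following from them. A reader cannot tell which ratio was meant. The natural guess is 1.00, the most favourable value there is, so if the claim fails there it fails everywhere.

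What is at stake is how the Part 1a intervals are read. A reader told that the part has 80% power or more may treat an interval that crosses 1.25 as meaningful evidence that a tablet differs from the capsule. If the real power is well below that, such an interval is a common result even when the true ratio lies comfortably inside the limits.

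**Working it through.** **Inputs.** From Section 9.2.1: 24 evaluable subjects, 27 randomised, CV 27.5%, limits 0.80–1.25, 90% confidence interval (two one-sided tests at 5% each). From Section 4.1: three periods and three sequences, every subject receiving all three treatments. Assumption: the CV is within-subject, as a crossover requires; the protocol does not say. The true ratio is not given, so a range is shown.

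**Standard error.** Log-scale SD = √ln(1 + 0.275²) = 0.270. SE of a treatment difference = 0.270 × √(2/24) = 0.0779.

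**Degrees of freedom.** With 24 complete subjects there are 72 observations. Removing 1 for the mean, 23 for subjects, 2 for periods and 2 for treatments leaves 44. An analysis of one tablet against the capsule alone would have 24 − 2 = 22. Both are shown.

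**Attempt to reproduce the plan's figure at ratio 1.00.** By normal approximation, ln(1.25)/SE = 0.2231/0.0779 = 2.863. Subtracting 1.645 gives 1.218, and power = 2Φ(1.218) − 1 = 2 × 0.8884 − 1 = 77.7%. Exact power, integrating over the estimated variance, is 75.9% (44 df) or 74.1% (22 df). The printed figure is not reproduced.

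Variants that exceed 80% all depart from the stated rule:
- one limit only: 88.8% on the log scale, or 80.9% on an untransformed ±20% scale
- 10% per side: 87.3%
- CV read as the SD of the within-subject difference: 98.0%
- 27 subjects instead of 24: see the table

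**Exact power at CV 27.5%** (two-treatment df to three-period df; 22 to 44 for n = 24, 25 to 50 for n = 27):

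| True ratio | n = 24 | n = 27 |
|---|---|---|
| 1.00 | 74.1–75.9% | 80.9–82.3% |
| 1.05 | 65.8–67.5% | 72.1–73.4% |
| 1.10 | 46.8–47.9% | 51.4–52.4% |
| 1.159 (Table 6 Cmax; illustration) | 23.8–24.3% | 25.9–26.3% |
| 1.162 (Table 6 AUC; illustration) | 23.0–23.5% | 24.9–25.4% |

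At ratio 1.00, 80% power needs 26 or 27 evaluable subjects, depending on the degrees of freedom, or a CV of no more than 26.0–26.4% with 24. At ratio 1.05 it needs 32 or 33.

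**Where 1.16 comes from.** Table 6 gives AUC(0–∞) 15.8/13.6 = 1.162 and Cmax 4.37/3.77 = 1.159, from 14 tablet and 15 capsule subjects. Using the table's between-subject CVs, about 14 pairs and an assumed within-subject correlation of 0 to 0.7, the 90% interval for AUC runs from 0.99–1.37 (correlation 0) to 1.06–1.28 (0.7). For Cmax it runs from 0.88–1.53 to 0.96–1.41.

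**Expected precision.** With n = 24 and 44 df, t = 1.680 and exp(1.680 × 0.0779) = 1.14. The 90% interval is the estimate times or divided by about 1.14. If the observed variability matches the assumption, an estimate above 1.25/1.14 ≈ 1.10 cannot satisfy the rule. An estimate of 1.16 would give about 1.16/1.14 = 1.02 to 1.16 × 1.14 = 1.32.

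**The case against.** The strongest defence is that nothing formal turns on the power figure. Section 9.1 and SAP Section 2.4 declare estimation. Section 9.2.1 admits that feasibility drove the numbers. SAP Section 7.1.3.2 plans point estimates and 90% intervals for Part 1a, and uses 0.80–1.25 as a criterion only for dose proportionality. The formulation choice rests on PK, safety and tolerability together. This stands, and it limits the consequence. It does not make the printed figure right, and it favours justifying the sample by precision.

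A second defence is that a lower CV would restore the power. At an assumed 20%, 24 subjects give about 97% at ratio 1.00, 90–91% at 1.05 and 70–71% at 1.10. That is true, but the claim is tied to 27.5%. A third is that 27 are randomised. The claim, however, is made for 24, and because each evaluable subject needs only one of the two tablets, a single comparison could have fewer.

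Two stronger readings are tempting, and the documents support neither.

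- A reader might infer from Table 6 that Part 1a really had about 23–24% power. Section 2.1 identifies the BTZ117349 tablet as the RC mesylate tablet, whereas Section 6.1 describes both Part 1a tablets as free base. The ratio divides summary geometric means from small groups. Its approximate interval includes 1.00 for Cmax at every correlation tried, and for AUC it includes or comes close to 1.00. Table 5, from a study that Section 4.5 lists among its capsule-dose sources, gives a 1500-mg single-dose AUC of 20.1. Set against that, the Table 6 tablet would have a ratio of 15.8/20.1 = 0.79. That comparison is across studies, but it shows that no stable planning ratio can be drawn from these tables.
- A reader might infer that the weak power undermined the decision on Part 1b. The similarity condition in Section 4.1 is nowhere defined as meeting 0.80–1.25, and Section 9.3.2 records that Part 1b had already been judged unnecessary by the time of Amendment 1.

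**Conclusion.** The power statement is wrong as written. It leaves out the true ratio, and no ratio delivers the stated power with 24 subjects at CV 27.5%. The shortfall is modest at ratio 1.00 (about 4 to 6 percentage points) and grows quickly: about 12 to 14 points at 1.05 and 32 to 33 at 1.10. This rests on reading the CV as within-subject and applying the stated two-sided rule. It does not depend on Table 6, which serves only as a labelled sensitivity case.

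The consequence is limited to the justification and to the reading of results. Estimates, intervals and conduct are unaffected. What matters is that an interval crossing 1.25 should not be reported as though it came from a comparison adequately powered to stay inside the limits.

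**What to change.** In Section 9.2.1, or in the study report if the protocol will not be amended again, replace the power claim with power at named true ratios for 24 evaluable subjects and a within-subject CV of 27.5%: about 76% at 1.00, 68% at 1.05 and 48% at 1.10 (three-period model). If 1.16 is shown, label it a sensitivity case taken from the mesylate tablet, with about 23–24% power.

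Give the expected precision as the main justification: a 90% interval equal to the estimate times or divided by about 1.14. State that the CV is within-subject.

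In the study report, interpret a Part 1a interval that crosses 1.25 through its estimate and width, not as evidence of dissimilar bioavailability.

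The cost is one paragraph of text and a less favourable stated power. Sample size, procedures and analyses stay as they are.
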